Table 9.1: Chronicity based on LBP-Impact averaged over months 10-12 of follow-up. Power for the overall F-test of equality of means under various alternative scenarios. (alpha = 0.05)

Alternative	SMT Alone	SSM Alone	SMT + SSM	Power
Additive	0.20	0.20	0.40	93%
Sub-Additive 1	0.25	0.25	0.35	91%
Sub-Additive 2	0.30	0.30	0.30	94%
Sub-Additive 3	0.25	0.25	0.25	81%
Single effect 1a	0	0.30	0.30	98%
Single effect 1b	0.30	0	0.30	94%
Single effect 2a	0	0.25	0.25	91%
Single effect 2b	0.25	0	0.25	80%

In this model a test of $H_0: \beta_5=0$ allows us to determine if there is strong evidence for synergistic or antagonistic effects associated with combined treatment.

Secondary Effectiveness Outcome of Chronicity: Chronic back pain: For a subject to be classified as a chronic back pain patient at the 1-year assessment they must endorse having “a back pain problem that has persisted at least 3 months and has resulted in pain on at least half of the days in the past 6 months”. This outcome is based on specific items

from the NIH Research Task Force recommended minimal data set:⁷³ Question 1 on LBP duration; and Question 2 on the proportion of days that LBP has been a problem in the past 6 months. To evaluate chronic back pain we will consider the 1-year status as a key secondary outcome for chronicity prevention, and will use the 6-month status as another key secondary outcome.

Chronicity Hypothesis: SMT alone will decrease the rate of cLBP by 6-9% from a baseline MC level anticipated to be 20% or higher. Similarly, SSM alone will decrease the rate of cLBP by 6-9%, and the combination of SMT+SSM will lead to an additive net reduction.

Secondary Chronicity outcome Analysis: The analysis of the secondary binary outcome will use parallel marginalized tests of the average SMT treatment effect and the average SSM treatment

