The overall SMT summary ($\beta_3 + \frac{1}{2} \beta_5$) estimates a common or average effect of SMT by pooling across sites, across risk groups, and across the two SSM arms (see figure 9.2). Similarly, $\beta_4 + \frac{1}{2} \beta_5$ estimates a common or average effect of SSM by pooling over the site, risk group, and SMT strata. Such analysis leverages the factorial design to permit separate estimates for each component of intervention. Notice that an additive model would use only 2 coefficient parameters to code the four treatment groups by assuming that the combined SMT+SSM group will have a treatment effect that is the sum of the effect for each individual component. Our analysis does not make any additive assumptions but rather directly defines a summary contrast for each treatment modality as the parameter of interest. Factorial designs are particularly efficient when evaluating two treatment modalities that work in complementary domains such as SMT (physical) and SSM (psychological) and permit separate assessment of each intervention. Formally, our primary analysis will separately test the null hypothesis $H_0: (\beta_3 + \frac{1}{2} \beta_5) = 0$ denoting no average effect of SMT, and $H_0: (\beta_4 + \frac{1}{2} \beta_5) = 0$ denoting no average effect of SSM. Each primary test will use a significance level of 0.05 without correction since each test evaluates a separate intervention. Finally, evaluation of the interaction term using $SMT_{ij} \cdot SSM_{ij}$ permits a formal evaluation for non-additivity by testing the interaction coefficient $H_0: \beta_5 = 0$ (interaction model described below).

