Power and Sample Size for Secondary Outcome of Chronicity: In order to determine the necessary sample size for effectiveness evaluation we need to formulate assumptions for the binary secondary outcome rate in the treated and untreated groups. [name] and Shekelle³⁴ review six studies conducted in primary care that focused on pain, functional status, or mixed outcomes. Using results from this paper we conservatively assume a rate of cLBP of 20% at 1 year. In order to formulate appropriate effect estimates we consider detection of a relative risk of RR=0.70 for each of SMT and SSM individually implying a reduction of the rate from 20% to 14% for these intervention groups. Based on the Cochrane Back Review Group¹⁴⁸ a relative risk of 0.70 is a clinically relevant and medium in size intervention effect, while the assumption of additive effects on the probability scale would lead to a cLBP rate of 8% among those randomized to SMT+SSM, which is considered a “large” treatment effect (RR=0.40). Therefore, we seek to design our study to detect and medium sized treatment effects, and consider power under a collection of plausible scenarios. A recent cohort study of acute LBP patients in primary care reported a similar proportion of patients with cLBP at 2 years, but noted the estimate varied based on the case definition¹⁴⁹ and estimates based on the NIH RTF definition are not yet available. Relative to general LBP patients, we expect a rate of chronicity in the MC group to be larger since we are enrolling subjects at an increased risk of chronicity. Accordingly, we increased the estimated proportion with cLBP in the MC group to be 30 and 40% and determined the magnitude of treatment effects for which we have $\geq 80\%$ power. At 1 year, we assume that we will have at least 88% follow-up based on prior studies conducted at the clinical research sites and studies^{11 150} with similar incentives¹⁵¹. Thus, with n=1000 enrolled subjects we expect at least n=880 total subjects available for primary analysis.

Our original sample size was chosen as n=1180 (since modified to n=1000) to ensure 80% power assuming an additive model with a chronic rate of 20% in UMC and a medium relative risk (RR) of 0.70. To evaluate power we conducted simulations using the R statistical package. We generated data under various additive assumptions. For analysis we first considered a single

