In 2021, the NIH statistician overseeing the trial raised the question of the adequacy of the planned adjustment for multiplicity given the trial's three main effectiveness objectives and accompanying four co-primary outcome measures. In response to this concern, the lead investigators recommended the recovery objective be changed to a key secondary outcome. Early in the conduct of the trial it was decided and approved as a protocol change to include patients that had an acute aggravation of ongoing LBP, if the ongoing pain was not rated as severe in the month prior to the aggravation. This protocol change substantially lowers the proportion of patients that can be expected to recover according to our criteria (pain severity = 0 and RMD score ≤ 2). Given this change, the recovery outcome was less appropriate as a primary effectiveness objective and demoting it to a secondary outcome mitigates the concern of cross-objective multiplicity control.

In 2022 NCCIH and the DSMB approved that the recovery effectiveness objective, formally one of the 3 primary effectiveness objectives, will be designated as a key secondary outcome.

[figure not shown]
Recovery Effectiveness Hypothesis: SMT alone will increase the rate of recovery by 5.5-7.5% or more from a baseline MC rate of 5%-15%. Similarly, SSM alone will increase the rate of recovery from 5.5-7.5%, and the combination of SMT+SSM will lead to an additive net increase in the recovery rate.

Recovery outcome definition: For a patient to be classified as recovered at the 6 month or 1 year assessment they must endorse both an NRS of 0, and an RMDQ of ≤ 2 .¹⁵² To evaluate recovery we will consider the 6-month status first and use the 1-year status second.

Recovery Analysis: The primary analysis will be two parallel tests of the average effects of SMT and SSM in a full logistic regression model for the primary outcome (recovery at 6 months). The primary analysis for recovery will use pre-specified linear contrasts for hypothesis testing regarding overall or average effects.

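### Additivity for chronicity is hypothesised in rates but tested on the log-odds scale, so exactly additive rates do not satisfy the null hypothesis of the planned interaction test

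*Combined protocol and SAP*

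**What the plan says.** All places are in section 9 of the combined protocol and SAP.

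- **Chronicity Hypothesis.** The effect is stated in rates: "SMT alone will decrease the rate of cLBP by 6-9% from a baseline MC level anticipated to be 20% or higher". SSM is given the same effect, and "the combination of SMT+SSM will lead to an additive net reduction".
- **Power and Sample Size for Secondary Outcome of Chronicity.** The scale is named. A relative risk of 0.70 is described as "implying a reduction of the rate from 20% to 14% for these intervention groups", and "the assumption of additive effects on the probability scale would lead to a cLBP rate of 8% among those randomized to SMT+SSM".
- **Secondary Chronicity outcome Analysis.** The Full Model is a logistic regression with SMT, SSM and their product (coefficient beta5), adjusted for site, risk group and period. The average effects are the contrasts beta3 + beta5/2 and beta4 + beta5/2. Including the product term also "permits a formal evaluation for non-additivity by testing the interaction coefficient", with null hypothesis beta5 = 0.
- **Recovery.** The hypothesis is again in rates: "the combination of SMT+SSM will lead to an additive net increase in the recovery rate". The Recovery Analysis paragraph specifies two average-effect tests from a full logistic model and writes out no interaction test.
- **Factorial Model Assumptions.** A possible interaction on the binary outcomes is described as synergistic or antagonistic, the latter meaning less than additive. No scale is given.
- **Power for chronicity, closing remarks.** The trial is stated not to be powered for interaction on the binary chronicity endpoint.

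**The concern.** Additivity depends on the scale. The hypothesis and the power scenario define it as rate reductions that sum. The planned test asks whether odds ratios multiply. If both therapies work, these conditions generally cannot hold together, so the state of affairs that the plan calls additive lies outside the null hypothesis of its own additivity test.

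The direction differs by outcome. With exactly additive rates, beta5 is negative in every scenario examined below. For chronicity, a bad outcome, a negative coefficient reads as extra benefit from combining the therapies. For recovery, a good outcome, it reads as a shortfall. At stake is how an interaction result on two key secondary outcomes is worded and understood. The main effectiveness conclusions are not at stake.

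**Working it through.** **Inputs.** Rates come from the two hypotheses and the chronicity power section. Arm sizes come from the LBP Impact power section: about 300 each for medical care and SSM and 200 each for SMT and SMT+SSM. With 90% follow-up that is 270/270/180/180. The plan states no alpha for the binary interaction test; 0.05 two-sided is assumed.

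**The plan's own figure first.** For 20% and relative risk 0.70, the plan states power of 72% (SSM) and 70% (SMT). Simulating 20/14/14/8 gives 72-74% and 73-74% with 900 evaluable, and about 72% for each (likelihood ratio test) with 880. If effects are instead additive on the logit scale, power is only 57-62% with 900. The stated power therefore rests on probability-scale additivity.

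**Expected coefficient when rates add exactly.**

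beta5 = logit(p_both) - logit(p_SMT) - logit(p_SSM) + logit(p_MC)

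For 20/14/14/8: -2.442 + 1.815 + 1.815 - 1.386 = -0.198, an interaction odds ratio of 0.82.

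For beta5 to be zero, the combined-arm odds would have to be (0.14/0.86)² / (0.20/0.80) = 0.106, a rate of 9.6% rather than the plan's 8%.

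**Precision in the design scenario.** SE = square root of the sum of 1/[n p (1 - p)] = √(0.0231 + 0.0308 + 0.0461 + 0.0755) = 0.419. The expected coefficient is 0.198/0.419 = 0.47 standard errors from zero.

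**Rejection of exactly additive rates.** Four binomial arms, saturated model, Wald tests, 200,000 simulated trials per row; trials with an empty cell (2.6% in the third row, almost none elsewhere) are left out of the logit column.

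| Outcome | MC / SSM / SMT / both (%) | beta5 | Logit test rejects | Risk-difference test rejects |
|---|---|---|---|---|
| Chronicity | 20 / 14 / 14 / 8 | -0.20 | 7% | 5% |
| Chronicity | 20 / 13 / 13 / 6 | -0.34 | 11% | 5% |
| Chronicity | 20 / 11 / 11 / 2 | -1.10 | 37% | 5% |
| Chronicity | 30 / 21 / 21 / 12 | -0.19 | 8% | 5% |
| Chronicity | 40 / 31 / 31 / 22 | -0.07 | 6% | 5% |
| Recovery | 5 / 10.5 / 10.5 / 16 | -0.32 | 10% | 5% |
| Recovery | 5 / 12.5 / 12.5 / 20 | -0.44 | 16% | 5% |
| Recovery | 10 / 17.5 / 17.5 / 25 | -0.20 | 8% | 5% |
| Recovery | 15 / 22.5 / 22.5 / 30 | -0.11 | 6% | 5% |

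The risk-difference test uses p_both - p_SMT - p_SSM + p_MC, which is zero in every row.

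**Effect of adjustment.** Adding a period term (180 per arm under full randomisation plus 90 + 90 under partial randomisation, an assumed split) leaves the logit rejection rates almost unchanged: 7% at 20/14/14/8, 11% at 20/13/13/6, 36% at 20/11/11/2, and 8% for recovery at 10/17.5/17.5/25. Site and risk group were not simulated.

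**The case against.** The strongest reply is that this hardly matters in practice, and much of that stands.

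- **Most trials would show nothing.** A reader might infer that additive effects will be reported as synergy for chronicity and antagonism for recovery. The numbers do not support that. In the design scenario about 93% of trials would find no significant interaction. The shift is in the expected coefficient, not in the typical test result.
- **The 37% is a corner case.** It pairs the largest hypothesised effect with the lowest control rate, leaving 2% in the combined arm, or 3.6 expected events among 180. The plan expects a control rate above 20% because it enrols people at raised risk. At 30% and 40% the distortion is small.
- **The plan already limits reliance on the test.** It disclaims power for binary interaction and points to the quantitative outcomes. Those use linear models, where a zero product term is additivity on the outcome's own scale.
- **Recovery is inferred.** No interaction test is written for it; it follows only from the full logistic model and the general remarks under Factorial Model Assumptions.
- **No decision rule is set.** Those remarks say that an interaction would be informative about how the therapies are used. They do not make any choice depend on it.
- **The average effects are sound.** A reader might extend the criticism to the average SMT and SSM contrasts because they are log odds ratios. Those tests are valid for the null of no average effect, and the scale on which they are reported is a matter of preference.
- **The cross-reference is loose.** The sentence on non-additivity points to an interaction model further down, and the only one written out after it is linear. The paragraph discusses the logistic Full Model, however, and that is the only model given for chronicity that contains the product term.

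None of this removes the mismatch. The test is planned, it is described as a test of non-additivity, and its null excludes the plan's own additive scenario. Low power does not cure a misplaced null.

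**Conclusion.** The mismatch is real and small in most settings. For chronicity, the test rejects exactly additive rates 6% to 11% of the time in the scenarios other than the 20/11/11/2 extreme, where it reaches 37%. If the same test were used for recovery, the figure would be 6% to 10% in most scenarios checked and 16% with a 7.5-point effect on a 5% base rate.

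These sizes assume the documents' rates and allocation, 90% follow-up, a two-sided 5% level, and models without site or risk-group terms. The sign of the expected coefficient follows from the rates alone.

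The finding is confined to the wording and scale of a supplementary interaction test on secondary binary outcomes. It does not touch the average-effect tests or the three primary outcomes.

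**What to change.** 1. Keep the full logistic model. From its fitted risks, standardised over site, risk group and period, test additivity for chronicity with p(SMT+SSM) - p(SMT) - p(SSM) + p(MC), using a delta-method or bootstrap interval.
2. State whether interaction will be tested for recovery. If so, use the same contrast.
3. Under Factorial Model Assumptions, tie the words synergistic and antagonistic to the risk-difference scale. If beta5 is also reported, label it as interaction on the odds-ratio scale.
4. Optionally, report the average SMT and SSM effects as risk differences beside the odds ratios, so that they can be read against the hypothesised 6-9 points.

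The cost is a few SAP sentences and routine post-estimation code, with no new data. The change should be made before treatment assignments are unblinded. It does not make the test powerful. In the design scenario the standard error of the contrast is √(0.16/270 + 0.1204/270 + 0.1204/180 + 0.0736/180) = 0.046, so 80% power needs a departure from additivity of about 2.8 × 4.6 = 12.9 points. A non-significant result should not be read as evidence that the effects add.

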Our primary analysis will test the global hypothesis that these three treatment comparisons are all null using a multivariate Wald test with 3 degrees of freedom and alpha=0.05. We will then provide individual confidence intervals for each coefficient that compares an intervention group to medical care based on Fishers least significant difference methods which provide individual nominal 95% confidence intervals and also estimates the simultaneous coverage probability.

Power and Sample Size for Primary Outcome of LBP Impact: To characterize the power of our primary analysis (an overall F-test) we provide a summary table that considers potential standardized mean differences comparing the individual intervention arms to medical care. For a small effect size (Cohen's d of 0.2) and an additive effect we have greater than 90% power to reject the null. However, additivity may not hold so we also consider sub-additive scenarios, and the scenario where only one intervention is effective. For small to moderate effect sizes (0.2 – 0.3 standard deviations) we have >90% with our proposed design. We assume n=1000 enrolled with a realistic 90% follow-up that yields 900 evaluated subjects. We also account for the

imbalanced design due to restricted randomization that will yield approximately 300 subjects in the UMC and SSM alone groups and 200 subjects in each of the SMT and SMT+SSM groups. Power is calculated based on 5,000 simulation replications for each scenario and presented in Table 9.1.

The current design is robust to the enrollment target and follow-up assumptions. For example, with an enrollment of n=1000 subjects and 85% follow-up we would have 90% power for our expected alternative scenario with small treatment effects (0.30 standardized mean difference) that are not additive (sub-additive 1).

A secondary evaluation will consider whether the separate effects of SMT and SSM are potentially additive and this will be done using a formal test for interaction:

$$\text{Interaction Model: } E(Y_{ij} \mid X_{ij}) = \beta_0 + \beta_1 \cdot \text{Site}(2)_j + \beta_2 \cdot \text{RiskGroup}_{ij} + \beta_3 \cdot \text{SMT}_{ij} + \beta_4 \cdot \text{SSM}_{ij} + \beta_5 \cdot \text{SMT}_{ij} \cdot \text{SSM}_{ij} + \beta_6 \cdot \text{Period}(2)_{ij} + \beta_7 \cdot \text{Period}(3)_{ij}$$

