effect using linear contrasts from a logistic regression model. Specifically, we will use two separate Wald tests based on logistic regression, with stratification by recruitment site and baseline risk group (medium, high). Let Y_{ij} denote the primary outcome status (0=not chronic; 1=chronic) for subject i in site j , and let $Site(2)$ be an indicator variable used to code the two recruitment sites. All analyses will adjust for site and the baseline risk status represented by $RiskGroup$ (0=medium risk; 1=high risk). In order to code the treatment groups we use the variables SMT (0=no; 1=spinal manipulation therapy), and SSM (0=no; 1=supported self-management). Given interruption by COVID-19 and period of restricted randomization we will adjust for this using the variables $Period(k)$ which will be an indicator for: 1=UG3 and UH3 through March 2020; 2=calendar period of restricted randomization; and 3=calendar period of resumed full factorial randomization. Regression models for the outcome are used to structure the probability of chronic back pain as follows:

$$Additive\ Model \quad \text{logit}[P(Y_{ij} = 1 | X_{ij})] = \beta_0 + \beta_1 \cdot Site(2)_j + \beta_2 \cdot RiskGroup_{ij} + \beta_3 \cdot SMT_{ij} + \beta_4 \cdot SSM_{ij} + \beta_5 \cdot Period(2)_{ij} + \beta_6 \cdot Period(3)_{ij}$$

$$Full\ Model \quad \text{logit}[P(Y_{ij} = 1)] = \beta_0 + \beta_1 \cdot Site(2)_j + \beta_2 \cdot RiskGroup_{ij} + \beta_3 \cdot SMT_{ij} + \beta_4 \cdot SSM_{ij} + \beta_5 \cdot SSM_{ij} \cdot SMT_{ij} + \beta_6 \cdot Period(2)_{ij} + \beta_7 \cdot Period(3)_{ij}$$

Our original application proposed using an additive model to generate a single summary parameter that describes the SMT effect (β_3) and the independent SSM effect (β_4). However, the additive model uses an assumption that the effect of one intervention is independent of whether the other intervention is delivered. Such an assumption is not necessary, and a full model can be used to make inference on a single linear contrast for each treatment that represents an average treatment effect.

The “Full Model” can then be used to derive an overall or average effect of SMT, and an overall or average effect of SSM. Specifically, focusing on the effect of SMT the model yields:

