likelihood ratio test of one treatment modality (either SMT or SSM). For simulations we considered crude analysis while our formal analysis will additionally adjust for site and baseline risk and therefore improve power since these are variables that only predict outcome and are not related to treatment group. For each scenario we simulated 5,000 data sets and empirically calculated power as the percentage of replicates in which the null hypothesis was rejected.

Using simulations with n=1000 subjects, 90% follow-up, and accounting for our imbalanced allocation due to COVID interruption we compute power for analyses that consider individual marginal treatment effects for both SMT and SSM. If we assume a UMC chronicity rate of 20% and a relative risk of 0.65 (rate under treatment = $20\% * 0.65 = 13\%$, or an absolute risk reduction of 7%) then we have >85% power to detect average SSM or SMT effects. If we a smaller effect corresponding to a relative risk of 0.70 (rate under treatment = $20\% * 0.70 = 13\%$, or an absolute risk reduction of 7%) then we have approximately 70% power to detect average SSM or SMT effects of this magnitude (specifically accounting for imbalance power is 72% for SSM and 70% for SMT). Power is greater for any relative risk when the UMC rate is increased to 30% or 40%. These relative risk effect sizes equate to medium effect sizes and are considered clinically important by Cochrane's Back Review Group.¹⁴⁸ We have not powered the study to detect interaction for the binary chronicity endpoint, but rather have powered the study to detect interaction on the underlying function and disability scales (see below).

Furthermore, we have excellent power to detect interaction effects where the effect of SMT and SSM may be synergistic or antagonistic, and using alpha=0.05 we have >80% to detect a X-point difference in LBP Impact treatment effects of one modality across the strata defined by the other treatment modality.

Secondary Effectiveness Outcome of Recovery: Determine the effectiveness of SMT, SSM, and the combination of SMT+SSM relative to medical care (UMC) in promoting recovery from acute or subacute LBP at 6 months.

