Power and Sample Size for the Recovery Outcome: In order to determine the necessary sample size for effectiveness evaluation we need to formulate assumptions for the primary outcome rate in the treatment and control groups. [name] et al.¹¹ compared SMT plus Home Exercise with Advice (HEA) to HEA alone among subacute and chronic patients and find complete recovery from leg pain in 20% of SMT+HEA versus 5% of HEA at 12 weeks, and 23% versus 12.5% respectively at one year (RR=1.84) providing evidence that relative risks in the range of 1.5-2.0 are plausible. The recovery rate at 6 months was estimated based on studies by Kamper et al.¹⁵² and members of our investigative team,¹⁵³ which used the same strict definition for recovery. Kamper et al.¹⁵² summarize recovery rates and criteria based on both NRS and RMDQ from four studies with acute and subacute subjects. Recovery rates range from 7% to 12%. A recent study by [name] et al.¹⁵³ reported a 5% recovery rate within a mixed population of sub-acute and

chronic patients with increased risk for cLBP. Given the potential uncertainty in the recovery rate for the MC group, we varied the expected recovery rate from 5-15% and determined the magnitude of treatment effects for which we have $\geq 80\%$ power.

For simulations we considered crude analysis while our formal analysis will additionally adjust for site and baseline risk yielding improved power since these are variables that only predict outcome and are not related to treatment group. For each scenario we simulated 5,000 data sets and empirically calculated power as the percentage of replicates in which the null hypothesis was rejected.

Figure 9.2 shows the power to test each intervention marginally. We see that we have >80% power to detect a relative risk of 1.75 associated with either SMT or SSM if the UMC recovery rate is 10%. If the UMC recovery rate is 5% then we have power to detect a 5.5% risk difference (RR=2.1), while if the UMC recovery rate is 15% then we have power to detect an 8.3% risk difference (RR=1.55). These effects are also medium in size and considered clinically important by Cochrane's Back Review Group.¹⁴⁸

Primary Effectiveness Outcome # 2 and 3: Determine the effectiveness of SMT, SSM, and the combination of SMT+SSM relative to medical care (MC) in achieving improvements in average pain intensity and back-specific functioning cumulative through 1 year based on monthly measures of RMDQ and weekly Pain NRS scores.

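### Stated power for chronicity and recovery comes from crude simulations, but the planned models adjust for Period; this costs SMT about 6 points for chronicity and 8 to 9 for recovery, and SSM nothing

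*Combined protocol and SAP*

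**What the plan says.** All references are to Section 9 unless stated.

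- **Chronicity power.** The current figures are introduced with "Using simulations with n=1000 subjects, 90% follow-up, and accounting for our imbalanced allocation due to COVID interruption". At a relative risk of 0.70 and a 20% control rate, "specifically accounting for imbalance power is 72% for SSM and 70% for SMT"; at 0.65, power is put above 85% for both.
- **What was simulated.** The same subsection describes the simulations as crude. It says the formal analysis adds site and baseline risk and will "therefore improve power since these are variables that only predict outcome and are not related to treatment group". The recovery subsection makes the same argument.
- **Recovery power.** At a 10% control rate, "we have >80% power to detect a relative risk of 1.75 associated with either SMT or SSM". Power is also claimed for a relative risk of 2.1 at 5% and 1.55 at 15%, against a criterion of at least 80%.
- **What will be fitted.** Under Secondary Chronicity outcome Analysis, "we will use two separate Wald tests based on logistic regression", and then "Given interruption by COVID-19 and period of restricted randomization we will adjust for this using the variables" Period(2) and Period(3), which appear in both logistic models. The August 2020 COVID-19 modifications extend the period adjustment to every analysis, so recovery is covered.
- **Restricted period.** Section 3.5 says that only SSM and MC were randomized from January to October 2021.

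**The concern.** The argument that covariate adjustment helps power rests on the covariates being unrelated to treatment. That is true of site and risk group, which are stratification factors. It is not true of Period, because nobody in the restricted period could receive SMT. Once Period is fitted, those patients say almost nothing about the SMT contrast, since there is no SMT patient in the same period to compare them with. SSM was randomized in every period and loses nothing.

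The power text allows for unequal arm sizes but nowhere for the Period term. It therefore presents SMT and SSM as nearly equally powered when the planned analysis is weaker for SMT. A null SMT result beside a positive SSM result could then be read as a difference between treatments when part of it is a difference in power.

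**Working it through.** **Inputs.** Alpha is 0.05 per test ("Each primary test will use a significance level of 0.05 without correction since each test evaluates a separate intervention"), taken as two-sided. Allocation comes from the LBP Impact power text: "imbalanced design due to restricted randomization that will yield approximately 300 subjects in the UMC and SSM alone groups and 200 subjects in each" SMT group. At 90% follow-up this gives 270 MC, 270 SSM, 180 SMT and 180 SMT+SSM. The surplus of 300 − 200 = 100 enrolled per arm is taken as the restricted period (90 per arm evaluated). Chronicity rates are 20%, 14%, 14% and 8%, additive on the probability scale as the plan assumes. (The n=1000 paragraph prints 20% × 0.70 as 13%; 14% is used here, as in the preceding paragraph.) No true period effect is assumed.

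**1. Reproduce the stated figures, crude.** Two-proportion test on the margins:
- SMT: 17% (n=540) against 11% (n=360); pooled SE 0.0240, unpooled SE 0.0231; power = Φ((0.06 − 1.96×0.0240)/0.0231) = 71.2%. Stated: 70%.
- SSM: 17.6% against 11.6% (n=450 each): 72.3%. Stated: 72%.

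Both are within 2 points, so the inputs are right and a crude analysis accounts for the figures.

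**2. Planned contrast, crude.** The average SMT effect on the logit scale is ½[logit(0.14) − logit(0.20)] + ½[logit(0.08) − logit(0.14)] = ½(−0.429) + ½(−0.627) = −0.528. Its variance is ¼ Σ 1/[n p(1−p)] = ¼(1/43.20 + 1/32.51 + 1/21.67 + 1/13.25) = 0.0439, so SE = 0.2095. Power = Φ(0.528/0.2095 − 1.96) = 71%.

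**3. Same contrast with Period.** Removing the restricted-period patients from the two no-SMT arms (180 left in each) is a close approximation: ¼(1/28.80 + 1/21.67 + 1/21.67 + 1/13.25) = 0.0506, SE = 0.2250, power = Φ(0.528/0.2250 − 1.96) = 65%. The full model with Period also gives 65%. SSM stays at 71% with or without Period.

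**4. Simulation of the planned Wald contrast.** SMT goes from 73–74% crude to about 67% with Period; SSM is 73% both ways. With restricted-period totals from 240 (310/310/190/190) to 160 (290/290/210/210), SMT with Period runs from 64% to 69% by simulation; the variance formula gives 63% at 240. Adding a prognostic risk group leaves it at 65–69%, so the gain from risk adjustment does not restore the loss.

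**5. Relative risk 0.65.** SMT is 86% crude and 81% with Period by the variance formula, and 83.5% with Period by simulation. Stated: above 85%.

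**6. Recovery, with n=1000 carried over.** SMT power:

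| MC rate / RR | Variance formula: crude → Period | Simulation: crude → Period | SSM (simulation) |
|---|---|---|---|
| 5% / 2.1 | 79% → 70% | 78% → 70% | 80% |
| 10% / 1.75 | 85% → 77% | 84% → 77% | 86% |
| 15% / 1.55 | 84% → 75% | 83% → 76% | 84% |

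Over the same range of restricted-period sizes, and across Wald and likelihood-ratio tests, SMT with Period is about 67–79%. At 5%, crude SMT power is already 76–79% depending on the test.

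**7. The August 2020 figure.** That text states 77% for SMT with n=1180 and up to 240 restricted. Then (1180 − 240)/4 = 235 per arm, plus 120 in MC and SSM, gives 355/355/235/235. At 88% follow-up the step 2 formula gives a variance of 0.0381 and power of 77%, matching the stated value. The step 3 formula gives 0.0441 and 71%. The earlier figure therefore also fits a crude analysis.

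**The case against.** Four objections deserve an answer.

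- **The crude label.** It closes the account of the n=1180 simulations; the n=1000 paragraph is separate. That the n=1000 runs were also crude is an inference. It is well supported: steps 1 and 7 reproduce the stated figures without Period, and the stated SMT–SSM gap of 2 points is smaller than the roughly 6 points that Period produces.
- **Recovery provenance.** This stands. The recovery subsection gives no sample size, follow-up or allocation, and Figure 9.2 is not shown. At n=1180 balanced with 88% follow-up (259.6 per arm), crude power is about 84%, 90% and 89%, consistent with the stated claims. A reader might infer that Period alone makes the recovery claims false. The documents do not support that: the figures may simply predate the current design, and at 5% the crude figure already falls short at n=1000.
- **The improvement sentence.** A reader might infer that the plan claims adjustment can only help, and so should drop the statement. It makes the claim for site and baseline risk only, where it is sound. The defect is that Period is not mentioned.
- **Consequence.** Both outcomes are secondary, and the sample size now rests on the quantitative primaries. The plan already discloses sub-80% chronicity power at 0.70 and expects a control rate above 20%. At 30% with a relative risk of 0.70 (30/21/21/12%), step 3 gives ¼(1/37.80 + 1/29.86 + 1/29.86 + 1/19.01) = 0.0365, an effect of −0.573 and SMT power of 85% even with Period. This limits the weight of the point but does not correct the stated figures.

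**Conclusion.** The point holds for SMT on the binary outcomes. Fitting Period costs SMT about 6 points of chronicity power at a relative risk of 0.70, leaving about 65–67% (range 63–69%), and takes it to about 81–84% at 0.65. Subtracting the recomputed 67% from the stated 70% suggests a loss of only 3 points, but that mixes two calculations; within either method the loss is about 6. At the small end of the restricted-period range, the result lies within a point of the stated 70%. At n=1000, SMT recovery power is about 70%, 77% and 76%, below 80% at all three control rates, with the caveat on provenance above.

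These sizes assume n=1000, 90% follow-up, 300/300/200/200 allocation, a restricted period of 160 to 240 patients and effects additive on the probability scale. The last matters: with a combined arm that is multiplicative or additive on the logit scale, recovery power with Period stays above 80% (85–95%) and chronicity falls to about 49–53%. Nothing here shows that the analysis itself is wrong; adjusting for Period is appropriate, and the power statement should reflect it.

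**What to change.** 1. Re-run the chronicity and recovery simulations with the planned full logistic model, including Period(2) and Period(3), the Wald test of each average effect, and the n=1000 imbalanced allocation.
2. State the assumed size of the restricted period, and the sample size, follow-up and allocation behind the recovery figures.
3. Report power separately for SMT and SSM for both outcomes, replacing the chronicity figures and the recovery claims of at least 80%.
4. Keep the sentence that adjusting for site and baseline risk improves power, and add that adjusting for Period reduces power for SMT because no SMT was allocated in the restricted period.

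The cost is a short simulation run and a few revised lines. The stated SMT power becomes less favourable. Design, tests, estimands and sample size are unchanged.
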